### **Stage 2 – Post-Investigation Assessment**

- What is your final diagnosis after results? (free text)
- Disposition decision
  - Hospitalize
  - Discharge
- What is your treatment and follow-up plan for the patient? (free text)

## Appendix E. Scoring Checklist for External Assessor with Gold Standard

### External Assessor Instruction:

Task: evaluate participants' responses in Kobo Toolbox against the gold-standard checklist for each case scenario. Score according to WHO and Uganda Clinical Guidelines.

How to score:

- Flag each item where the participant's response matches or is clinically equivalent to the gold standard.
- Leave blank if the response is absent, incorrect, or inappropriate.
- Do not infer beyond what is explicitly written by the participant.

Domains:

- Diagnostics: Correct if all indicated tests are ordered and unnecessary tests are avoided.
- Treatments: Correct if the participant specifies the correct plan, dose/volume, delivery/reassessment, and avoids harmful or unnecessary therapies.
- Diagnosis, triage, and disposition: Correct if the participant's answer matches the gold-standard label/category for the scenario.

### Assessor sheet format (same for all cases):

- Participant ID: (assigned after randomization)
- Case ID:
- Correct guideline-adherent management items
  - ☐ Triage Category
  - ☐ Immediate Treatments
  - ☐ Investigations
  - ☐ Diagnosis
  - ☐ Disposition
  - ☐ Treatment and follow-up plan

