## **C.4. Sample Size**

This pilot study will use a feasibility-based sample size, determined by the total number of OPD clinicians available at [name] Hospital. We anticipate enrolling approximately 16 participants, representing all nurses, clinical officers, and nursing assistants currently working in the OPD of [name] Hospital. Each participant will complete 12 simulated scenarios, yielding an estimated 192 scenario-level observations. While not powered to detect small effect sizes, this sample is deemed to be sufficient to assess feasibility, refine study procedures, and provide preliminary effect estimates to inform the design and power calculations of a subsequent larger trial.

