## **C.6. Randomization and allocation**

Participants will be randomized to the order of study conditions—App-assisted (intervention) vs. standard practice (control)—using computer-generated permuted blocks of size 2, stratified by cadre (nurse/nursing assistant vs clinical officer) to ensure balance across professional groups. The randomization list will be computer-generated in advance by a member of the research team not involved in recruitment or outcome assessment and stored in a password-protected master sheet. Participant IDs will be assigned sequentially after written consent in order of recruitment; each ID is then linked to a pre-specified condition sequence from the master sheet.

To control for case content and ordering effects, matched scenario pairs were created for each condition (A-set for one period, B-set for the other period), with random assignment of A vs. B to the first or second period per participant. Within each period, the case order (1–6) was independently randomized. Thus, for every participant the master sheet specifies: (i) intervention sequence, (ii) period assignment of A vs. B cases, and (iii) the randomized within-period case order.

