### C.7. Intervention and Control

Experimental arm (OASES App): Participants will use the OASES tablet-based CDSS, which incorporates the Interagency Integrated Triage Tool (IITT) and three condition-specific algorithms (diarrhea, dyspnea, and seizures) derived from WHO and Uganda Clinical Guidelines. No formal training sessions will be conducted; however, participants will receive a brief orientation walk-through of the App immediately prior to its use.

Control arm (standard practice): Participants will manage simulated cases without the App, relying on their usual knowledge and clinical experience. Standard resources available in OPD, including paper-based versions of the IITT and Uganda Clinical Guidelines, will be available for reference.

All participants will complete both arms using a crossover design, with a washout period of at least one week between conditions. During the washout, participants will return to their normal OPD duties without access to the OASES App. No additional clinical teaching or training will be provided during the study period.

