### C.8. Simulation and Scenarios

Each participant will complete 12 facilitated clinical vignette scenarios, with six scenarios per study arm (two diarrhea, two dyspnea, and two seizures). Scenarios will be adapted from WHO training materials for emergency care (e.g., *Basic Emergency Care* course, *Emergency Triage Assessment and Treatment* guidelines) and tailored to reflect common emergency presentations in the OPD of [name] Hospital. Both adult and pediatric cases will be included, varying in severity and presentation to capture the spectrum of conditions typically encountered. Draft cases will undergo expert review and pilot testing with representative clinicians to ensure clarity, realism, and contextual relevance. Cases will be designed in matched pairs to ensure comparable content and difficulty between study periods, with equivalence determined by expert review and pilot testing. Scenarios will be balanced for complexity, number of critical actions, and expected completion time.

Cases will be delivered verbally by a trained facilitator, who will respond only to participant questions to simulate real-world information gathering. Facilitators will log which key history and examination items are elicited using a structured tick-box script.

At two predefined points in each vignette, participants will record their diagnostic and treatment plan:

1. Initial assessment stage – working impression, immediate treatments, and diagnostic tests ordered.
2. Post-investigation stage – final diagnosis, disposition decision, treatment plan and follow-up plan.

Each participant's simulation session will last approximately one hour. All sessions will be scheduled during off-duty hours to ensure voluntary participation and to avoid disruption of patient care.

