### C.10. Data Collection and Management

Data will be collected electronically using Kobo Toolbox, an open-source, web-based platform developed by the Harvard Humanitarian Initiative for data collection in resource-limited and field settings (<https://www.kobotoolbox.org/>).

- Baseline data: Prior to randomization, participants will complete a baseline survey capturing demographic and professional characteristics, prior emergency training, and digital literacy (**Appendix B**).
- Simulation data: During each vignette, two facilitators (emergency medicine clinicians from the study team) will deliver cases, log process measures using structured tick-box forms (**Appendix C**), and capture start/end times. Any discrepancies will be reconciled immediately after the session. Participants will record clinical decisions directly into Kobo Toolbox forms at predefined stages (**Appendix D**).
- Outcome scoring: Responses will be exported in de-identified forms and scored by two independent assessors, blinded to allocation, using pre-defined gold-standard answer keys (**Appendix E**). The two assessors will be two clinicians not involved in App or case development. Discrepancies will first be discussed by the two reviewers to reach consensus; if disagreement persists, a third senior adjudicator (not involved in App or case development) will provide the final decision.
- Post-simulation survey and interview: After completing sessions that involve App use, participants will complete a structured electronic questionnaire assessing usability (SUS), perceived usefulness, trust, satisfaction, and feasibility (**Appendix F**). To complement these quantitative measures, the two facilitators will also conduct brief semi-structured interviews with each participant immediately after their simulation session (**Appendix G**). Interviews will not be audio-recorded; instead, facilitators will take contemporaneous field notes, which will be expanded into detailed summaries for subsequent qualitative analysis.

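### The assessor sheet carries the Participant ID, so blinded assessors can link one person's 12 forms across both conditions: an avoidable risk to blinding, not a demonstrated failure

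*Combined protocol and SAP*

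**What the plan says.** Section C.10 gives the blinding claim for outcome scoring: "Responses will be exported in de-identified forms and scored by two independent assessors, blinded to allocation". Section C.9 says the same for the primary outcome, where the assessors turn free text into binary items.

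The assessor sheet in Appendix E has one format for every case. Its first two fields are "Participant ID: (assigned after randomization" and the Case ID. The participant response form in Appendix D has the same two fields. Under section C.6 there is one ID per participant, given out sequentially and tied to a condition sequence in the master sheet.

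The design links case set to condition within a person. Section C.6: "A-set for one period, B-set for the other period), with random assignment of A vs. B to the first or second period per participant". Section C.7: "All participants will complete both arms using a crossover design". Section C.8 has each participant complete 12 scenarios, "with six scenarios per study arm (two diarrhea, two dyspnea, and two seizures").

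Two safeguards are stated in C.10: the de-identified export, and assessors who had no part in building the App or the cases. Section D explains de-identification as the absence of names and personal identifiers. Nowhere do the documents describe a code per form, a masked Participant ID or a shuffled scoring order.

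**The concern.** De-identified is not the same as unlinkable. With the Participant ID on each sheet, an assessor can put one person's 12 forms side by side. A clue on any one of them can then carry over to forms that hold no clue themselves.

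This matters because participants and facilitators know when the tablet App is in use, so blinded scoring is the main protection for the primary outcome. The crossover analysis of that outcome is the only confirmatory analysis (C.11). The scoring involves judgement: Appendix E credits answers that are clinically the same as the key, and it asks for several elements at once under treatments. Knowing the arm could tip a borderline call. Cohen's κ and consensus would not reveal this, because both assessors see the same link and could lean the same way.

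A clue is plausible. The participant instructions in Appendix C say that the App suggests treatments and tests, and the participant then writes free text.

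**Working it through.** **1. Number of forms.** From C.4: "We anticipate enrolling approximately 16 participants" and "Each participant will complete 12 simulated scenarios, yielding an estimated 192 scenario-level observations". 16 × 12 = 192, which reproduces the plan's figure. From C.8, 6 + 6 = 12 forms per participant, so 16 × 6 = 96 App forms and 96 control forms.

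**2. Is set tied to condition within a participant?** There are two condition orders and two set orders:

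| Condition order | Set order | A-set cases | B-set cases |
|---|---|---|---|
| App, control | A, B | App | control |
| App, control | B, A | control | App |
| control, App | A, B | control | App |
| control, App | B, A | App | control |

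In all four rows the 12 forms split six and six. Given the set of each case, the arm of one form fixes the arm of the other 11. Before any clue the assessor cannot say which block is App, because set order is randomised per participant. For the same reason, a clue about one participant does not reveal the arm for another.

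**3. What the sheet adds.** Assessors need a case identifier to choose the answer key. They do not need the Participant ID, which is what joins the 12 forms.

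**4. Size, as an illustration.** Let q be the probability that an App form is recognised as such. The documents give no value, so q is assumed. Also assume that only App forms can give the clue, that recognition is independent between forms, and that one clue exposes all 12 linked forms.

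- Linked: share of all forms exposed = 1 − (1 − q)^6.
- Unlinked: only the recognised form is exposed, so the share = 96q / 192 = q / 2.

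| q (assumed) | Linked share | Linked, of 192 | Unlinked share | Unlinked, of 192 |
|---|---|---|---|---|
| 1% | 5.9% | 11.2 | 0.5% | 1.0 |
| 5% | 26.5% | 50.9 | 2.5% | 4.8 |
| 10% | 46.9% | 90.0 | 5.0% | 9.6 |
| 20% | 73.8% | 141.7 | 10.0% | 19.2 |
| 30% | 88.2% | 169.4 | 15.0% | 28.8 |

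For example, 1 − 0.9^6 = 0.469 and 1 − 0.8^6 = 0.738.

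**5. Clustering.** Copying App phrases may be a personal habit, so independence leans high. Take a beta-binomial with an assumed within-person correlation of 0.5, that is a + b = 1 and a = q. The probability of no clue in six forms is the product of (b + i)/(1 + i) for i = 0 to 5.

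- q = 10%: 0.9 × 1.9 × 2.9 × 3.9 × 4.9 × 5.9 / 720 = 0.777, so 22% of forms are exposed.
- q = 20%: 0.8 × 1.8 × 2.8 × 3.8 × 4.8 × 5.8 / 720 = 0.592, so 41% are exposed.
- Full clustering: the linked share is q itself, 10% or 20%. That is still twice the unlinked q / 2.

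**The case against.** The strongest reply is that nothing shows that answers will betray the arm, and several features work against it. Participants in both arms type into the same Kobo form, so any layout of the App does not carry over. The App's content comes from WHO and Ugandan guidelines, and control participants have paper copies of the IITT and the Uganda guidelines, so guideline phrasing can appear in either arm. The assessors did not help to build the App, and nothing shows that they know its wording. Fuller answers may hint at the App, but they are also what is being scored. This stands: recognition is possible, but its rate is unknown.

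Second, carrying a clue over to all 12 forms needs an assessor who recognises it with confidence, knows or works out the tie between set and condition, groups the forms, and has not yet scored them. It also needs the set of each case to be visible. A reader might infer that Case IDs are coded by set, because the one ID shown is A001. That fits the A and B labels in C.6, but no B-set ID appears and no text states the coding rule. This stands too, and it makes the linked figures upper-end values.

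Third, discretion is limited. Assessors may credit only what is explicitly written, the key is specific, triage and disposition are fixed choices, and a third clinician adjudicates. These features narrow the room for bias but do not remove it for free-text management items, and they do not answer why the Participant ID is on the sheet.

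**Conclusion.** The point holds as an avoidable weakness in the blinding procedure. As written, the sheet links 12 forms that split six and six between conditions, and neither stated safeguard breaks that link.

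A reader might infer that blinding is already lost, or that one tell-tale answer is bound to expose all 12 forms. The documents support neither: they give no recognition rate, they do not establish set-coded Case IDs, and they do not say that the assessors will know the design.

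At an assumed q of 10% (20%), linkage could expose up to 47% (74%) of forms under independence and certain inference, 22% (41%) with the assumed correlation of 0.5, and 10% (20%) with full clustering. Without linkage the figure is 5% (10%). The linked share is thus larger by a factor of 2 to about 9 (46.9 / 5.0 = 9.4) at q of 10%. These figures count forms exposed; the resulting bias in scores cannot be estimated from the documents. The sample size and the analysis model are unaffected. The words in brackets after the ID field are not the fault; the fault is the same ID on every form from one person.

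**What to change.** On assessor copies, replace the Participant ID with a random code that is unique to each response form. Keep a case identifier so that the answer key can be chosen. Neutral case numbers are optional: once forms are unlinked, the set letter says little, because set order is randomised per participant. Present the forms case by case, shuffled over participants, and without submission metadata. The last item is a precaution, because the assessor instruction in Appendix E refers to responses in Kobo Toolbox, although neither the response form nor the assessor sheet lists a timestamp. The holder of the randomisation list keeps the file that links codes to participants and restores the link after scoring is final.

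Sections C.9 and C.10 and Appendix E should state this. The cost is a short export and re-linking step, to be set up before scoring starts. It adds no burden for participants and does not alter the analysis.

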## Abstract

**Background:** Emergency conditions such as severe diarrhea, dyspnea, and seizures remain major causes of morbidity and mortality in low- and middle-income countries. Despite available World Health Organization (WHO) and national guidelines, adherence in rural outpatient departments (OPDs) is often suboptimal. The Organization for the Advancement and Support of Emergency Systems (OASES) App is a clinical decision-support system (CDSS) developed in 2025 by the University of Milano-Bicocca as part of a quality improvement collaboration with [name] Hospital, Kalongo, Uganda. The App digitizes validated WHO-based triage and emergency care algorithms for offline use in resource-limited hospitals, but it has not yet undergone formal testing and evaluation by intended end-users.

**Objective:** To evaluate the effectiveness, usability, and feasibility of the OASES App among frontline clinicians during simulated emergency scenarios.

**Methods:** This pilot study will employ a prospective, randomized, stratified crossover simulation design at [name] Hospital. Approximately 16 OPD clinicians (nurses, clinical officers, nursing assistants) will complete 12 facilitator-led standardized scenarios (diarrhea, dyspnea, seizures), randomized between App-assisted and standard practice conditions with a  $\geq 7$ -day washout. Primary outcome is clinicians' adherence to evidence-based guidelines for diagnostics and treatments. Secondary outcomes include triage accuracy, diagnostic accuracy, disposition decision appropriateness, process quality, case completion time, and user perceptions of usability, trust, and feasibility. Quantitative data will be analyzed using mixed-effects models, while qualitative feedback will undergo thematic analysis.

**Expected Outcomes:** Findings will provide preliminary evidence on the effectiveness and acceptability of the OASES App, inform App refinement, and support the design of a subsequent powered clinical evaluation.

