### C.9. Outcomes

Primary outcome:

- Guideline-adherent management: Proportion of pre-specified, guideline-consistent critical management actions (diagnostics and treatments) completed per vignette (proportion 0-1). Participant responses recorded at the initial assessment and post-investigation stages will be scored against a gold-standard answer key derived from WHO guidelines (Basic Emergency Care assessment checklists, ETAT performance checklists, Integrated Management of Childhood Illness checklists). Scoring will be performed by two independent assessors, blinded to allocations, mapping free text to binary items (performed correctly vs. not performed/incorrect). Disagreements will be resolved by consensus.

Secondary Outcomes:

- Triage accuracy: Correct assignment to Interagency Integrated Triage Tool (IITT) category (Red/Emergency, Yellow/Urgent, Green/Non-urgent) compared with the case-specific expected category (binary). Scoring will be performed by two independent assessors, blinded to allocations.
- Disposition appropriateness: Appropriateness of the disposition decision (hospitalize, discharge) compared with case-specific expected disposition in the answer key, based on

WHO/Uganda guidelines (binary). Scoring will be performed by two independent assessors, blinded to allocations.

- Diagnostic accuracy: Correctness of working impression (initial stage) and final diagnosis (post-investigation stage), compared with case-specific diagnostic labels in the answer key, based on WHO/Uganda guidelines (binary). Scoring will be performed by two independent assessors, blinded to allocations, mapping free text to binary items (performed correctly vs. not performed/incorrect).
- Guideline-adherent evaluation (process quality): Proportion of critical history and examination items elicited by the participant during the vignette, compared with case-specific list of critical items derived from WHO guidelines (proportion 0-1). Scoring will be performed by two facilitators during each simulation session using the facilitator tick-box logs.
- Time to completion: Duration needed to complete each vignette, measured by facilitators (continuous).
- Usability: Total score on System Usability Scale (SUS), a widely validated 10-item tool for evaluating software systems in healthcare and other fields (continuous).

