### C.11. Statistical Analysis

All analyses will follow the intention-to-treat principle. For vignette-level outcomes, if a participant does not complete an entire scenario, that scenario will be excluded from analysis. Within completed scenarios, missing or blank responses will be treated as incorrect (i.e., non-adherent), on the assumption that an unanswered item reflects lack of knowledge or failure to act. For survey outcomes, only available responses will be analyzed, with no imputation. Descriptive statistics will therefore be based on the number of participants who provided a response to each item. The number of missing scenarios and survey responses will be reported.

The primary analysis will follow a crossover design, with each participant contributing observations under both study conditions (App-assisted vs. control) across distinct but content-equivalent case scenarios:

- Guideline-adherent management: Analyzed as a bounded proportion (0-1) using a generalized linear mixed-effects model with binomial distribution and logit link. The model will include fixed effects for study arm (App vs. control), period (first vs. second session), sequence (allocation order), scenario type (diarrhea, dyspnea, seizure), cadre (clinical officers vs nurses), years of experience (continuous), baseline comfort in using mobile Apps (dichotomous). Random intercepts will be specified for participant to account for repeated measures. Results will be reported as adjusted mean differences with 95% CIs. Inter-rater reliability will be assessed using Cohen's  $\kappa$  for individual items and intraclass correlation coefficients (ICC) for total checklist scores.
- Triage appropriateness, disposition appropriateness, and diagnostic accuracy: Each will be analyzed as binary outcomes (correct vs. incorrect) using mixed-effects logistic regression, with the same fixed and random effects structure as above. Results will be reported as adjusted odds ratios with 95% CIs. Inter-rater agreement will be evaluated using Cohen's  $\kappa$ .

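### The primary outcome covers diagnostics and treatments only, but the assessor sheet puts its name over six boxes, three of them secondary outcomes, and no rule says which boxes count

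*Combined protocol and SAP*

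**What the plan says.** **Definition.** C.9 defines guideline-adherent management as "Proportion of pre-specified, guideline-consistent critical management actions (diagnostics and treatments) completed per vignette (proportion 0-1"). The Abstract agrees: "Primary outcome is clinicians' adherence to evidence-based guidelines for diagnostics and treatments". It then lists the rest separately: "Secondary outcomes include triage accuracy, diagnostic accuracy, disposition decision appropriateness, process quality".

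**Analysis.** C.11 fits a binomial mixed model to the primary proportion but does not give the number of items per vignette. The other three outcomes have their own models: "Triage appropriateness, disposition appropriateness, and diagnostic accuracy: Each will be analyzed as binary outcomes (correct vs. incorrect"). C.11 also makes the crossover analysis of the primary outcome the sole confirmatory analysis and labels the secondary outcomes exploratory.

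**Scoring form.** Appendix E has one form, "Assessor sheet format (same for all cases"). Under the line "Correct guideline-adherent management items" it lists six tick boxes: Triage Category, Immediate Treatments, Investigations, Diagnosis, Disposition, and Treatment and follow-up plan.

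**Scoring rules.** The Appendix E instructions word the management domains as joint conditions. Diagnostics are "Correct if all indicated tests are ordered and unnecessary tests are avoided". For treatment the rule is "Treatments: Correct if the participant specifies the correct plan, dose/volume, delivery/reassessment, and avoids harmful or unnecessary therapies". Diagnosis, triage and disposition form a third domain, scored by matching a label.

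**The concern.** The form that generates the primary data carries the primary outcome's name over a set of items wider than the outcome's definition. An analyst who follows the form would divide ticks by six. One who follows C.9 would use three boxes, or would look for a list of actions that the form does not hold. The two routes can give different values for the same vignette, and nothing in the plan chooses between them.

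This matters because only this outcome is confirmatory. With the item set left open, it could be settled after scores are known, and exploratory outcomes could enter the confirmatory result. C.4 also intends the pilot's effect estimates to inform the power calculation of a larger trial, so an ambiguous score would carry forward. The effects on the two groups of boxes may well differ, since the App contains a dedicated triage algorithm as well as the condition modules.

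**Working it through.** **Inputs from the documents**
- Participants: about 16; scenarios per participant: 12 (C.4).
- Boxes on the sheet: 6 (Appendix E).
- Boxes within the C.9 definition: 3 (Immediate Treatments, Investigations, Treatment and follow-up plan).
- Boxes that are separate secondary outcomes: 3 (Triage Category, Diagnosis, Disposition).

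The word diagnostics in C.9 cannot readily be stretched to cover the Diagnosis box, because the Appendix E rules keep tests ordered and diagnosis reached in different domains.

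**Step 1. The plan's own figure.** 16 × 12 = 192 scenario-level observations, as C.4 states.

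**Step 2. Items behind the primary score.**
- Six boxes: 192 × 6 = 1152 binary items, or 576 per condition.
- Three boxes: 192 × 3 = 576 binary items, or 288 per condition.
- Share of the sheet outside the C.9 definition: 3/6 = 50%.

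**Step 3. One vignette scored both ways.** Suppose triage, diagnosis and disposition are right and all three management boxes are wrong.
- Six boxes: 3/6 = 0.50.
- Three boxes: 0/3 = 0.00.

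**Step 4. Effect on the raw proportion scale.** Let d1 be the mean App effect on the three management boxes and d2 the mean effect on the other three. The six-box effect is (3·d1 + 3·d2)/6 = (d1 + d2)/2. The plan states no effect sizes, so those below are assumptions.

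| Assumed d1 | Assumed d2 | Three-box effect | Six-box effect |
|---|---|---|---|
| 0.20 | 0 | 0.20 | 0.10 |
| 0 | 0.20 | 0 | 0.10 |
| 0 | 0.30 | 0 | 0.15 |
| 0.20 | 0.20 | 0.20 | 0.20 |

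The first two rows give the same six-box result for opposite findings on the defined outcome. The last row shows that the choice does not change the mean effect when d1 = d2.

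**Step 5. Triage alone.** A 0.20 effect on the triage box and none elsewhere gives 0.20/6 = 0.033, or about 3.3 points.

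**Step 6. Granularity if only three boxes count.** Three binary items allow four values: 0, 1/3, 2/3 and 1. The treatment rule joins four conditions: plan, dose or volume, delivery or reassessment, and avoidance of harmful or unnecessary therapy. Suppose each is met independently with probability q (an assumption). The chance of a tick is then q^4:
- q = 0.8: 0.8^4 = 0.41, against a component-level proportion of 0.80.
- q = 0.9: 0.9^4 = 0.66, against 0.90.

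Read strictly, a box score and a proportion of actions are therefore different quantities. C.9 describes the latter, and C.8 treats the count of critical actions as a property on which scenarios are balanced. The sheet does not record that count.

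**The case against.** The strongest reply is that the sheet is a shared form with a loose heading. The same kind of blinded assessors score the primary outcome, triage, disposition and diagnosis, so one page for all of them is natural. The Abstract and C.9 exclude the three boxes from the primary outcome, C.11 models them separately, and the Appendix E rules put them in their own domain. The sheet has no total line, whereas the facilitator form in Appendix C has an explicit score out of 8. Because boxes are ticked singly, either score can be computed later.

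Most of this stands. A reader might infer that the plan makes the primary score ticks out of six. The documents never give that formula, and the shared-form reading is at least as plausible. What the reply does not supply is a rule: no section drops the three boxes or states a denominator, and the heading points the other way. C.11 also plans intraclass correlations for total checklist scores, and the six-box sheet is the only assessor checklist shown for this outcome.

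On granularity, composite boxes are a legitimate choice. They penalise unnecessary tests and therapies, which a plain list of actions would miss. The instructions also accept clinically equivalent answers, so whether one omitted component fails a box is inferred from the wording. A three-item score still lies between 0 and 1, and C.9 sets no minimum number of items. These points make separate rows a preference. They do not make the sheet an itemised record of critical actions.

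**Conclusion.** The point holds as an unresolved conflict over how the primary score is built. The definition covers diagnostics and treatments; the form puts the outcome's name over six boxes, half of them other outcomes; nothing states the item set or the denominator. The possible size is 0.50 against 0 for a single vignette in the extreme case, and a six-box effect equal to the average of the two group effects. The 20- and 30-point effects and the component probabilities are illustrations, not document figures.

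Three stronger readings are not supported:
- **That the confirmatory outcome is in fact half exploratory.** This follows only if the heading is taken at face value.
- **That an App effect on triage alone could pass as a substantial management effect.** At 20 points it moves a six-box score by about 3.3 points; a 10-point shift needs 20 points on triage, diagnosis and disposition together.
- **That the form is defective because the example key separates treatment plan from follow-up plan.** The participant form asks for both in one question, and the assessor box mirrors it.

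The conflict should still be settled before scoring, because it concerns the only confirmatory outcome and a later choice could be made with scores in view.

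**What to change.** Before scoring starts:
1. State in C.9, C.11 and Appendix E that the primary proportion uses diagnostic and treatment items only, and give the denominator for each case.
2. On the assessor sheet, move triage, diagnosis and disposition under their own heading so that they feed only their secondary outcomes.
3. Preferably, list the critical diagnostic and treatment actions in each case key as separate binary rows, with rows for avoiding unnecessary tests or therapies, so that the score matches C.9. Only the A001 key is shown, so the number of rows in the other cases has to come from their own keys.

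Items 1 and 2 remove the main conflict with a few sentences and a changed heading. Item 3 also closes the gap between boxes and actions, at the cost of slightly more assessor time per form. No new data are needed, because the diagnostic and treatment responses are collected as free text and can be scored against the revised sheet.
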